Södra Älvborgs Hospital, Borås, Sweden

e-mail: [contact]

[name]

Frölunda sjukhus, Västra Frölunda, Sweden

e-mail: [contact]

Summary

Background

Stress related ill health is today a common cause for long term sick leave among women in their midst of life as well as being a common cause for visits to the primary health care.

Aim

To investigate the effect on mental health, quality of life and sick leave of education provided within the primary health care given in group or individually for women aged 45-60 years with stress related symptoms.

Methods

This is a randomised controlled clinical trial using a two factor design.

Education is given as four sessions exploring menopause, physiology, oestrogen deficiency, cardiovascular health, consequences of stress, mental health, relationships, sexuality and lust as well as potential actions to improve the situation. In addition, the group sessions will touch base on topics like obstacles and resources, coping strategies, and behavioural changes.

The individual education will be person-centred and given as five sessions focusing on stress related symptoms, ill health, physiology and coping strategies.

Expected result

If any of these two interventions turns out to be successful it may provide low cost intervention options for a common problem often seen in primary health care.

Study protocol: Effect of primary care education on mental health, quality of life, need for sick leave and health care consumption in women 45-60 years with stress-related symptoms. A randomized controlled trial.

Introduction

Stress-related ill health is today the most common cause of long-term sick leave in women in the middle of life and a common cause of primary care visits (1). It is clear that women suffer from long-term sickness and ill health to a greater degree than men (2). Women's physical and mental health in Sweden shows a marked decrease in the ages of 45-60 years (3). During this life phase, called menopause, the woman undergoes a hormonal transformation (3). Stress-related symptoms appear after a long time with high stress load without sufficient recovery (4). There are currently few studies with high evidence-based treatment on stress-related symptoms (5). Busch et al show in an evaluation that 70% of people who have undergone rehabilitation overall are satisfied with the treatment. The treatment, on the other hand, has not led to increased return to work (6).

Research shows that women often lack information about physical and mental and urogenital changes under the "middle of life" / menopause (7).

Group education is a method and participation in group education can be a good way for women to get information and exchange experiences (8).

Earlier studies evaluating patient education in hypertension and diabetes show significant improvement (9.10). Talking can raise awareness about choices and consequences, create insight into behaviours and provide insight into the overall life situation to find the core of ill health (11). Arving et al shows that health-related quality of life increased faster in patients receiving support calls than those who received normal treatment (12).

There is a lack of primary care studies that evaluate the effect of education in group and / or individually for women 45-60 years with stress-related symptoms.

The vast number of middle aged women with ill health and subsequent high risk for disease risk and increasing number of long-term sick leave shows that it is important to study women's health in this age group.

Aim

To study the effect of education in a group or individually delivered in primary health care on mental health, quality of life and sick leave in women aged 45-60 with stress-related symptoms.

Research questions

- A. Is there any effect of group information (GI) on quality of life, mental health, sick leave or visits to a primary health care centre compared to a control group?
 1. What is the effect of group education (GI) on quality of life (measured by change in scores in SF36 from baseline to 6 months after completed intervention) –
Primary research question (other questions are secondary).

Study protocol: Effect of primary care education on mental health, quality of life, need for sick leave and health care consumption in women 45-60 years with stress-related symptoms. A randomized controlled trial.

2. What is the effect of group education (GI) on quality of life (measured by change in scores in SF36 from baseline to 12 months after completed intervention)
3. What is the effect of group education (GI) on change in number of days on sick leave. (At baseline the number of days on sick leave up until present time is stated by women currently being on sick leave. At the 6 month follow the same information is retrieved is retrieved. The change is the difference between these measurements.)
4. What is the effect of group education (GI) on change in number of days on sick leave. (At baseline the number of days on sick leave up until present time is stated by women currently being on sick leave. At the 12 month follow the same information is retrieved is retrieved. The change is the difference between these measurements.)
5. What is the effect of group education (GI) on depressive mood (measured by change in scores in MADRS from baseline to 6 months after completed intervention)
6. What is the effect of group education (GI) on depressive mood (measured by change in scores in MADRS from baseline to 12 months after completed intervention)
7. What is the effect of group education (GI) on stress levels (measured by change in scores in PSS-14 from baseline to 6 months after completed intervention).
8. What is the effect of group education (GI) on stress levels (measured by change in scores in PSS-14 from baseline to 12 months after completed intervention).
9. What is the effect of group education (GI) on stress levels (measured by change in scores in HAD from baseline to 6 months after completed intervention).
10. What is the effect of group education (GI) on stress levels (measured by change in scores in HAD from baseline to 12 months after completed intervention).
11. What is the effect of group education (GI) on visits to primary health care? (women are asked at baseline if they had to visit the primary health care center during the preceding two months. The same question is asked at 6 months. The measurement is the change in proportion of women who visited the primary health care center).
12. What is the effect of group education (GI) on visits to primary health care? (women are asked at baseline if they had to visit the primary health care center during the preceding two months. The same question is asked at 12 months. The measurement is the change in proportion of women who visited the primary health care center).
- B. Is there any effect of structured person-centered support (PCS) on quality of life, mental health, sick leave or visits to a primary health care centre compared to a control group?
13. What is the effect of Structured person-centered support (PCS) on quality of life (measured by change in scores in SF36 from baseline to 6 months after completed intervention)?
14. What is the effect of Structured person-centered support (PCS) on quality of life (measured by change in scores in SF36 from baseline to 12 months after completed intervention)?
15. What is the effect of Structured person-centered support (PCS) on change in number of days on sick leave. (At baseline the number of days on sick leave up

Study protocol: Effect of primary care education on mental health, quality of life, need for sick leave and health care consumption in women 45-60 years with stress-related symptoms. A randomized controlled trial.

until present time is stated by women currently being on sick leave. At the 6 months follow the same information is retrieved is retrieved. The change is the difference between these measurements.)

16. What is the effect of Structured person-centered support (PCS) on change in number of days on sick leave. (At baseline the number of days on sick leave up until present time is stated by women currently being on sick leave. At the 12 months follow the same information is retrieved is retrieved. The change is the difference between these measurements.)
17. What is the effect of Structured person-centered support (PCS) on depressive mood (measured by change in scores in MADRS from baseline to 6 months after completed intervention)?
18. What is the effect of Structured person-centered support (PCS) on depressive mood (measured by change in scores in MADRS from baseline to 12 months after completed intervention)?
19. What is the effect of Structured person-centered support (PCS) on stress levels (measured by change in scores in PSS-14 from baseline to 6 months after completed intervention)?
20. What is the effect of Structured person-centered support (PCS) on stress levels (measured by change in scores in PSS-14 from baseline to 12 months after completed intervention)?
21. What is the effect of Structured person-centered support (PCS) on stress levels (measured by change in scores in HAD from baseline to 6 months after completed intervention)?
22. What is the effect of Structured person-centered support (PCS) on stress levels (measured by change in scores in HAD from baseline to 12 months after completed intervention)?
23. What is the effect of Structured person-centered support (PCS) on visits to primary health care (women are asked at baseline if they had to visit the primary health care center during the preceding two months. The same question is asked at 6 months. The measurement is the change in proportion of women who visited the primary health care center)?
24. What is the effect of Structured person-centered support (PCS) on visits to primary health care (women are asked at baseline if they had to visit the primary health care center during the preceding two months. The same question is asked at 12 months. The measurement is the change in proportion of women who visited the primary health care center)?

Methods

Selection of patients, inclusion criteria and logistics

Women, 45-60 years old, reached through advertisements in newspapers and on a website, are offered to participate in the study. Application for participation in the study is made electronically via Fou Primary Care Södra Älvborg website or by telephone to research nurse. Inclusion criteria:

Study protocol: Effect of primary care education on mental health, quality of life, need for sick leave and health care consumption in women 45-60 years with stress-related symptoms. A randomized controlled trial.

- a. The woman has some mental and / or physical health problems such as depression, anxiety, gastrointestinal symptoms, muscular symptoms and / or cardiovascular symptoms.
- b. The woman has been on sick leave for a maximum of 30 days in the last two months.
- c. The woman has no major language difficulties that prevent understanding and speaking Swedish language as well as filling in forms.
- d. Woman lacks serious illness such as psychosis, severe depression or dementia
- e. The woman is not treated in palliative care
- f. The woman has no ongoing drug or alcohol abuse.

Research nurse contacts the woman via telephone and provides further information about the study where the opportunity is given to ask questions. If the woman meets all inclusion criteria and choose to accept the study, electronically self-administered questionnaires about self-assessed health and health-related quality of life will be sent to all participants, as well as a written informed consent that is signed. Self-administered questionnaires and consent kits are filled in via link on R & D Primary Care Södra Älvborg's website.

The research nurse is responsible for administration of questionnaires and arranging physical check-up.

Group allocation

Research randomizer is used to generate a random series based on block-randomization in blocks of four. The random series is transferred to closed sealed opaque envelopes, each containing group assignment. The manufacture of these closed envelopes is done by a person who is not involved in the study.

Randomization occurs after the woman answered all questionnaires at baseline. Then the research nurse opens the next sealed numbered envelope and the patch inside describes what group the woman is allocated to:

- Group 1: group information (GI)
- Group 2: group information (GI) + person-centred support (PCS)
- Group 3: person-centred support (PCS)
- Group 4: no GI or PCS (control group)

Intervention

Group information (GI).

Midwives and district nurses participate as group leaders. Each group training includes 12 women and comprises four one-and-a-half hours of information with topics related to physical and mental changes in the body as well as conversations aimed to make behaviour, consequences of behaviour and choices in life conscious.

Study protocol: Effect of primary care education on mental health, quality of life, need for sick leave and health care consumption in women 45-60 years with stress-related symptoms. A randomized controlled trial.

The first group event contains education with the definition and myths of "middle of life" / menopause, physiology, menstrual cycle, hormonal conversion, local oestrogen deficiency symptoms, osteoporosis and information on treatment options and self-care advice.

The second group event contains teaching and information on cardiovascular health, its risk and health factors, physiology, mental health, relationships, sexuality and lust as well as information on treatment options and self-care advice.

The third group event contains insights into stress-related ill health, physiology, social relationships in family and work, sexuality and lust, insight into obstacles and resources, coping strategies and behavioural changes to promote health.

The fourth group event contains insights on relationships, sexuality and lust as well as a summary of "How do we want to live to feel good?" Insight into obstacles and resources, coping strategies and behavioural changes to promote health.

Structured person-centred support (PCS):

Individually structured person-centred education is carried out by a district nurse or midwife. It includes five sessions. The conversation contains dialogue on symptoms of stress-related ill health, what is happening in the body (physiology), relationships, coping strategies, requirements, guilt, exercise and diet. Women randomized to receive both group education and individual education will receive group education first.

Control

The research nurse informs women in all groups that they can contact the primary health care centre if they wish to explore what can be offered from there. If the woman contacts the health care centre, they are treated according to the health care centre's current routines. Hence, any education or treatment provided outside the scope of this research project can vary between health care centres. Group education and individual education for the other groups are provided on top of the primary health care centre's standard measures.

Data collection

The following information is collected at baseline.

- Demographic data: age, work, education, family situation, hormone treatment, cardiovascular disease, stress disorder, cause of healthcare contact (psychological and / or physical) and prior sick leave days. In addition, they are asked if they have visited the healthcare centre for the past two months as a patient and, if so, for what (a number of standard symptoms can be selected)
- Blood pressure: blood pressure with electronic blood pressure cuff, if necessary manual blood pressure, the mean of two blood pressure is recorded at the time of visitation.
- MRS: measures the occurrence of menopausal symptoms. The questionnaire consisting of 11 questions brings together menopause symptoms in three main groups; somatic symptoms, urogenital symptoms and mental symptoms. The questionnaire

Study protocol: Effect of primary care education on mental health, quality of life, need for sick leave and health care consumption in women 45-60 years with stress-related symptoms. A randomized controlled trial.

indicates the severity of symptoms on a 5-degree scale. Low incidence of symptoms indicates 0 points and high incidence of symptoms 4 points. Total sum, individual questions and three subgroups are reported. The instrument has been tested for reliability and validity (14).

- MADRS: investigates the degree of depression and depressive symptoms. The questionnaire consists of 9 questions, which are graded on a 6-degree scale where 0 points indicate a low incidence of symptoms and 6 points indicate a high incidence of symptoms and ill health. The instrument has been tested for reliability and validity (15).
- SF-36: examines physical and mental health as well as changes over time. The questionnaire consists of 36 multiple-choice questions, divided into eight subdivisions. Scores are between 0 - 100, higher value indicates better health experience. The instrument has been tested for reliability and validity (16).
- HAD: investigates the degree of anxiety and depressive symptoms. The form consists of 14 questions with seven issues that measure anxiety (HAD-A) and seven issues that measure depression (HAD-D) and graded on a 4-degree scale. Each question can yield between 0 and 3 points and summed to give a score scale of 0-21 for respective anxiety and depressive symptoms. Higher points indicate higher incidence of symptoms. The instrument has been tested for reliability and validity (17).
- s-UMS, self-assessed fatigue syndrome. Identify individuals who have developed or may be developing a clinical fatigue syndrome with impaired work ability and increased risk of sick leave. The form has four questions with queries. The instrument has been tested for reliability and validity (18).
- PSS-14: Measurement of self-assessed general perceived stress. how often you have experienced life as unpredictable, uncontrollable and congestive in the last month. The form has fourteen questions. The Swedish translation has shown good internal validity (19).
- AUDIT: self-assessment test for alcohol consumption and consists of ten questions divided into three domains: consumption, addiction and alcohol-related injuries. Results above the cut-off limit 6 points for women and 8 points for men indicate a risky drinking. The instrument has been tested for reliability and validity (20).

Follow-up of intervention takes place six and twelve months after completion of treatment / education. Midwife and district nurse participate in the follow-up. During this visit, follow-up of quality of life, mental health, care needs and sick leave is made by the woman filling in the same questionnaire as at baseline.

Data is collected by the research nurse at baseline and six and twelve months after completion of education. Returned questionnaires are encoded and code lists will be filed at the R & D unit Södra Älvborg in a locked and fireproof archive for more than ten years. Code key is stored separately. Access to the material has project managers and supervisors. Electronic stored data is stored on the computer's network device H so it is backed up automatically, not on the workstation hard drive. Data is stored on the Västra Götaland region password-protected computer. Tape and video recordings are not used.

Study protocol: Effect of primary care education on mental health, quality of life, need for sick leave and health care consumption in women 45-60 years with stress-related symptoms. A randomized controlled trial.

Statistical analysis

Questionnaires are summarized according to manuals. Data is described descriptively with appropriate estimates. The scientific research questions will be analysed by multivariate regression where the two interventions GI and PCS, each being an independent variable, is entered a two-factor model, where interaction effects between the two interventions is also evaluated. Moreover, age becomes an independent confounding variable. A regression is made for each outcome measure (each scientific question). The level of significance is set to ≤ 0.05 . IBM SPSS version 20 or later will be used.

Sample size estimation

Sample size estimations are made for research questions 1, 3 and 5. When estimating sample size, we assume a significance level of 0.05, power of 0.80 and that we do a two-way test. When estimating sample sizes, we use simple group comparison for two independent groups with Mann-Whitney's test as surrogate test.

Research question	Assumptions	Assumed "Effect size"	Number required
1 (primary)	We assume that the quality of life increases by three points in the intervention group and zero points in the control group. Furthermore, the standard deviation is eight in both groups.	0,38	236
3	We assume that days on sick leave decrease by two days in the intervention group and by 0.5 days in the control group. Furthermore, the standard deviation is five days in both groups.	0.30	368

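### Follow-up is dated from an undefined completion of education, so women who stop attending and all controls have no stated assessment date

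*Combined protocol and SAP*

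**What the plan says.** Research question A.1, the primary question, takes the change in SF-36 "measured by change in scores in SF36 from baseline to 6 months after completed intervention". The other SF-36, MADRS, PSS-14 and HAD questions use the same anchor at 6 or 12 months. The sick-leave and health-care-visit questions mention only a 6- or 12-month follow-up, but the Data collection section ties all of it to completion: "Follow-up of intervention takes place six and twelve months after completion of treatment / education", and again "Data is collected by the research nurse at baseline and six and twelve months after completion of education".

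Under Group allocation, "Randomization occurs after the woman answered all questionnaires at baseline", so any completion of education comes after randomisation. There are four groups: GI, GI plus PCS, PCS, and a control group with neither. Under Intervention, GI "comprises four one-and-a-half hours of information" and PCS has five sessions. The combined group receives GI first, which makes nine sessions in sequence.

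The Statistical analysis section enters the "two interventions GI and PCS, each being an independent variable" in a two-factor regression, evaluates their interaction and includes age. The document does not define completion. It gives no follow-up date for a woman who stops or for a control woman, and it states no analysis population, missing-data method or dropout allowance.

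**The concern.** Whether a woman completes four, five or nine sessions is decided after randomisation and may be related to how she is doing. If her follow-up starts only on completion, whether she contributes an outcome depends on that event. Group 4 has no sessions, so its follow-up must be dated in some other way, which the plan leaves open. If the research nurse follows controls on a convenient date but has nothing due for a woman who left after two sessions, Groups 1 to 3 lose a selected subset and Group 4 does not. The comparison of the women with data would then no longer be protected by randomisation. Recruiting more women would not repair it, and questionnaires never sent cannot be recovered at analysis.

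**Working it through.** **The plan's own figure.** Inputs from Sample size estimation: difference 3, SD 8, two-sided 0.05, power 0.80, Mann-Whitney test. The normal formula 2 × (1.96 + 0.842)² × (8/3)² gives 112 per group. Dividing by the Mann-Whitney efficiency 3/π gives 118 per group, or 236 in total, as stated. The inputs below are therefore the plan's own.

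**Group size.** The plan uses "block-randomization in blocks of four" for four groups. Equal allocation is inferred, so 370/4 = 92.5 per group.

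**Assumptions not in the documents.** Education has no true effect. A share p of each education group stops and is not assessed. All controls are assessed. Stoppers change by d SF-36 points less than completers. The SD stays at 8. The central case is p = 20% and d = 4 (half the SD).

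**Bias in one group.** With no effect, the whole education group has the same mean as controls, which is the completers' mean minus p × d. Completers therefore exceed controls by p × d = 0.20 × 4 = 0.8 points, and 0.8/3 = 27% of the assumed effect.

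**Group 1 versus Group 4.** This is also the GI coefficient when both factors are coded 0/1 and the interaction is in the model.
- Women left in Group 1: 92.5 × 0.8 = 74.
- SE = 8 × √(1/74 + 1/92.5) = 1.248, and 0.8/1.248 = 0.641.
- Two-sided rejection = Φ(−1.96 + 0.641) + Φ(−1.96 − 0.641) = 9.8%.

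**GI main effect, equal loss in Groups 1 to 3.** This averages Group 1 minus Group 4 and Group 2 minus Group 3.
- Bias = ½ × [0.8 + (0.8 − 0.8)] = 0.40 points. Group 3 is on the non-GI side and has lost stoppers too, so half of the bias cancels.
- SE = ½ × 8 × √(3/74 + 1/92.5) = 0.906, ratio 0.44, rejection 7.3%.
- Fitted without the interaction term, the model gives 0.42 points and 7.5%.

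**GI main effect, more loss in Group 2.** Two independent 20% chances to stop give 1 − 0.8² = 36%, leaving 59.2 women.
- Group 2 bias = 0.36 × 4 = 1.44, so the main effect is biased by ½ × [0.8 + (1.44 − 0.8)] = 0.72 points.
- SE = ½ × 8 × √(2/74 + 1/59.2 + 1/92.5) = 0.936, ratio 0.77, rejection 12%.

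**Range for Group 1 versus Group 4.**

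| p | d | bias (points) | false-positive rate |
|---|---|---|---|
| 10% | 2 | 0.2 | 5.3% |
| 20% | 4 | 0.8 | 9.8% |
| 30% | 6 | 1.8 | 28% |

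With d = 0 there is no bias. With d negative the bias has the same size and the opposite sign.

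**Power is not the issue.** Under 20% loss in Groups 1 to 3, 3 × 74 + 92.5 = 314.5 women remain. Power for the pooled GI contrast falls only from 94% to 90%.

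**The case against.** The strongest reply is that nothing in the plan excludes anyone. The timing sentences are impersonal and completion is undefined. GI is a fixed course of four events for groups of 12, so completion could mean the end of the course whoever attended. This stands: a reader might infer that the plan compares completers with all controls, but no sentence says that women who stop are dropped from follow-up or analysis.

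A reader might also infer that controls are safe from this loss. Read equally literally, the text gives Group 4 no completion date either, so controls lack an assessment date just as stoppers do. The asymmetry arises only if controls are given a date in practice and stoppers are not.

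Two further inferences lack support. The first is that GI and PCS would be coded as received. The trial is described as randomised with two factors, and the plan simply does not state the coding. The second is that the bias favours education. Stoppers may be more burdened, but some women may stop because they feel better.

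Finally, 0.8 points and 9.8% describe Group 1 versus Group 4 only. The main effect of a two-factor model gives a different answer that depends on coding and on the loss in Group 2.

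The reply does not supply a date. The timing rule as written gives none for stoppers or controls, and nothing elsewhere in the document replaces it.

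**Conclusion.** The concern holds as a defect in the follow-up rule, not as a demonstrated completer analysis. The primary outcome and all later assessments are anchored to an undefined post-randomisation event. Women who stop and all controls have no stated assessment date, and no analysis population closes the gap. Selective loss from the education groups is therefore possible under the text.

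Its size and direction cannot be derived from the documents, which give no attendance rate and no difference between completers and stoppers. In the illustrative central case the primary comparison is biased by 0.4 to 0.8 points against an assumed effect of 3, with a false-positive rate of 7% to 12% depending on the contrast and on the loss in Group 2. These figures rest on the assumed p and d, on stoppers going unassessed and on controls being fully assessed. If stoppers are followed and analysed, this source of bias is zero.

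**What to change.** In the outcome questions and the Data collection section, date the 6- and 12-month assessments in all four groups by a rule that does not depend on attendance. Two rules would serve: count from randomisation, or count from a scheduled end date assigned to every woman, controls included, at randomisation. Counting from the last scheduled session is not enough, because Group 4 has no sessions.

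State that the questionnaires are collected from every randomised woman unless she withdraws consent to data collection, and that stopping the education is not withdrawal from follow-up. In the Statistical analysis section, state that GI and PCS are coded as randomised.

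The cost is protocol and SAP wording, plus some extra contact and existing follow-up visits for women who stopped. The Data collection section has a midwife and district nurse take part in those visits, so this is more than posting a form, but it needs no new procedure and no additional women. Some stoppers will not respond, and the estimated effect may be smaller than among completers.

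### The sick-leave outcome (questions 3, 4, 15 and 16) gives no value for women not on leave and no look-back window, so the question 3 sample-size row is unsupported

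*Combined protocol and SAP*

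**What the plan says.** Research questions, A.3: "At baseline the number of days on sick leave up until present time is stated by women currently being on sick leave". The follow-up clause reads "At the 6 month follow the same information is retrieved is retrieved", and the outcome is the difference between the two figures. Question 4 (12 months) and questions 15 and 16 (person-centred support) use the same definition.

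Other relevant places in the combined protocol and SAP:

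- Methods, recruitment: "Women, 45-60 years old, reached through advertisements in newspapers and on a website, are offered to participate in the study". Inclusion criterion b: "The woman has been on sick leave for a maximum of 30 days in the last two months". This is a ceiling on leave; no criterion sets a minimum.
- Research questions, A.11, on health-care visits: "women are asked at baseline if they had to visit the primary health care center during the preceding two months". That outcome has a fixed window and is not limited to a subgroup.
- Data collection: the demographic items include previous sick-leave days, with no window and no link to the four questions. The same questionnaire is repeated at follow-up. "Follow-up of intervention takes place six and twelve months after completion of treatment / education".
- Statistical analysis: one regression per research question; how women not on leave enter it is not stated.
- Sample size estimation, question 3: "We assume that days on sick leave decrease by two days in the intervention group and by 0.5 days in the control group". The effect size is 0.30, the number required is 368 and the planned total is 370. On the spread, the row says only this: "Furthermore, the standard deviation is five days in both groups". No source for the SD and no dropout allowance are given.

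**The concern.** Sick leave is one of the three outcomes named in the aim, and question 3 carries the largest of the three sample-size requirements. The definition describes the length of the current spell among women who have one. It is silent on the woman who is working at baseline, at follow-up or at both.

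Three readings fit the text, and they differ in who is analysed, in whether the comparison is still randomised, and in whether the question 3 row applies. Unless a rule is written somewhere outside these documents, it would have to be chosen at analysis, possibly with the data in view. At least one reading removes the women in whom the intervention worked as hoped, namely those who went back to work.

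**Working it through.** **1. The plan's own figures.** Inputs from Sample size estimation: two-sided 0.05, power 0.80, Mann-Whitney test. Take the t-test n per group, divide by the Mann-Whitney efficiency 3/π, round up and double.

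- Question 1: d = 3/8 = 0.375; 112.6 × π/3 = 117.9, giving 118 per group, **236**.
- Question 3: d = (2 − 0.5)/5 = 0.30; 175.4 × π/3 = 183.7, giving 184 per group, **368**.
- Question 5: d = 1.6/4.90 = 0.3265; 148.3 × π/3 = 155.3, giving 156 per group, **312**.

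All three stated numbers are reproduced. At 185 v 185 on this basis, power is 0.94 for question 1 and 0.80 for question 3 (0.82 with a t-test).

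**2. Reading 1: on leave at both visits.** A woman who returns to work, or who starts leave later, has no change score. Membership of the analysis set depends on the outcome after randomisation. A woman on one unbroken spell can only show a rise, so the assumed mean fall of two days could come only from new, shorter spells. The documents do not allow the size of the bias to be calculated.

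**3. Reading 2: on leave at baseline, 0 on return.** The comparison stays randomised, but new leave is missed. The row needs 368/370 = 99.5% of recruits on leave. The documents do not give the share on leave. With assumed shares, and d = 0.30 carried into the subgroup:

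| Assumed share on leave | Women | Power |
|---|---|---|
| 10% | 37 | 0.14 |
| 20% | 74 | 0.24 |
| 50% | 185 | 0.51 |

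**4. Reading 3: all women, 0 when not on leave.** The headcount is 370 against 368, two women to spare. Criterion b limits a fall to about 30 days. A rise has no such limit: follow-up is six months after the education ends, so a woman still on her baseline spell scores about 6 × 30 = +180 days or more.

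*The row can be met.* Suppose a share p of the GI arm falls by s days, p/4 of the control arm does the same, and everyone else scores 0. Choosing ps ≈ 2 gives the assumed means of −2 and −0.5. Simulated t-test power at 185 v 185 (20,000 runs) is 0.996 for 20% with 10 days, 0.96 for 13.8% with 14.5 days, 0.88 for 10% with 20 days and 0.71 for 6.7% with 30 days.

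*It is fragile to long spells.* In an arm of 185 with mean m, let one woman score L and all others share one value. The smallest possible SD is (L − m) × √185/184.

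- m = −2: L = 60, 90, 180 gives 4.6, 6.8, 13.5. SD 5 is reached at L = 65.6.
- m = −0.5: L = 60, 90, 180 gives 4.5, 6.7, 13.3. SD 5 is reached at L = 67.1.

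*Effect on the mean comparison, with the row's means held.* The other 184 women are taken as normal with SD 5 and shifted so that the arm mean stays at −2. The arm variance is then about 24.9 + (L + 2)² × 185/184². The estimated SE is √[(arm variance + 25)/185], and significance needs a difference above 1.966 × SE. The observed difference has mean 1.5 and true SE about 0.52, because the long spell is a fixed value.

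| One woman at | Arm variance | Threshold (days) | Power |
|---|---|---|---|
| none | 25.0 | 1.02 | 0.82 |
| +60 | 45.9 | 1.22 | 0.71 |
| +90 | 71.1 | 1.42 | 0.56 |
| +180 | 205.9 | 2.20 | 0.09 |

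Placing her in the control arm instead gives 0.71, 0.57 and 0.09.

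**The case against.** The best defence is that reading 3 is the obvious one: a woman not on leave has 0 days of current leave, and 368 against 370 shows that everyone was meant to count. That is probably right, but it is not written, and the text as it stands limits the item to women on leave. The baseline item on previous sick-leave days may already hold what is needed. The form is not in the documents, however, the item has no stated window, and the four questions do not refer to it.

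A second defence is that any assumed SD may prove wrong, and the SD of 8 for the primary question is unsourced too. That stands. It is why a reader should not infer that the 368 is miscalculated or that every reading contradicts it: the arithmetic is exact, and short spells under reading 3 meet the row.

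A third concerns the outlier illustration. A reader might infer that one long spell always destroys power. Adding one without holding the means also changes the effect: in the GI arm at +60, +90 or +180 it shrinks the 1.5-day difference to about 1.17, 1.01 or 0.51 days, and in the control arm it enlarges it. That mixes two things, so the table above holds the means. Where one woman is simply replaced on otherwise normal data, Mann-Whitney power, the basis of the sizing, stays at about 0.77 to 0.83. The exposure belongs to the planned regression on the mean; the sizing test does not share it in that setup.

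The powers under reading 2 rest on assumed shares and on an effect size that could be larger among women on leave. They illustrate a risk and do not demonstrate a shortfall.

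**Conclusion.** The definition is incomplete, and followed literally it is a wrong rule, because it drops women who return to work. That conclusion comes straight from the text and is firm. The consequences for power are conditional:

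- the share on leave and the spell lengths are assumptions;
- the SD limits (about 66 or 67 days to pass 5; at least 13.3 at +180) need only 185 women per arm and the row's own means;
- the power figures with long spells also assume normal data for the other women.

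The question 3 row is unsupported, not refuted. A reader might also infer that the trial as a whole is at risk. The documents do not support that: sick leave is secondary, and the 370 exceeds the 236 for the primary question. The point should be fixed before analysis, at low cost.

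**What to change.** At baseline, 6 and 12 months, record for every woman the number of sick-leave days in the preceding two months, 0 if none. Criterion b and the visit questions already use this window. The change then lies between about −30 and about +60 days.

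Reword questions 3, 4, 15 and 16 accordingly. State that all randomised women are analysed on this count, adjusted for its baseline value; a robust or bootstrap standard error is an option for the skew. Re-derive the question 3 row with a justified SD and a stated follow-up loss, or withdraw its 80% power statement. For scale, 10% loss with the row's own assumptions would need 368/0.9 = 409 women.

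Cost: one questionnaire item and four research questions change, with no extra patients; 370 still exceeds 236 and 312. Leave outside the windows, including the full length of long spells, is not captured, which matters in a trial motivated partly by long-term leave. One woman at +60 can still weigh on the mean (power about 0.71 above). If baseline collection has begun, the baseline value depends on what the existing sick-leave item or the criterion b check recorded; the documents do not say whether that number is kept.
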